2.6 Analysis supporting secondary objectives

Analysis of endpoints supporting secondary objectives is described in Sections 2.6.1 – 2.6.6 below.

2.6.1 Secondary endpoint(s)

Secondary endpoints include the following:

- Achieving immune response (responder) as defined by a positive SARS-CoV-2 qualitative IgG antibody assay at other assessment time points ≥ 14 days after full course (2 doses) vaccination (yes/no).
- Immune conversion (yes/no) which is defined as:
 - Pre-vaccination absence of SARS-CoV-2 qualitative IgG antibody with post-vaccination positive SARS-CoV-2 qualitative IgG antibody assay at any assessment time point ≥ 14 days after full course (2 doses) vaccination (yes/no); or
 - Pre-vaccination serum presence of SARS-CoV-2 quantitative IgG antibody with post-vaccination ≥ 4 -fold increase in SARS-CoV-2 quantitative antibody titer as determined by dilution assay at any assessment time point ≥ 14 days after full course (2 doses) vaccination (yes/no); or
 - Initial negative SARS-CoV-2 nucleocapsid antibody at Visit 2 (Day 1) with post-vaccination positive SARS-CoV-2 qualitative IgG antibody assay at any post-Visit 2 (Day 1) assessment time point ≥ 14 days after full course (2 doses) vaccination (yes/no) (Applicable to Cohorts 4 and 5.)

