## **Amendment 2**

### **Amendment Rationale**

This protocol has been amended to allow participants with a known diagnosis of COVID-19 prior to starting in the study to be enrolled. In this amendment we have also addressed inconsistencies and sought to make clarifications at certain points.

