## 8 Visit schedule and assessments

The below Assessment Schedules ([Table 8-1](#), [Table 8-2](#), [Table 8-3](#), [Table 8-4](#), [Table 8-5](#) and [Table 8-6](#)) list all assessments with an X when they are performed. All data obtained from these assessments must be supported in the participant's source documentation. The "X" in the table denotes the assessments to be recorded in the clinical database or received electronically from a vendor. The "S" in the table denotes the assessments that are only in the participant's source documentation and do not need to be recorded in the clinical database.

Participants should be seen for all visits/assessments as outlined in the assessment schedules or as close to the designated day/time as possible. The Investigator should promote compliance by instructing the participant to attend the study visits as scheduled and by stating that compliance is necessary for the participant's safety and the validity of the study. Missed or rescheduled visits should not lead to automatic discontinuation. The participant should be instructed to contact the Investigator if he/she is unable for any reason to attend a study visit as scheduled or if he/she is unable for any reason to take the study treatment as prescribed.

Participants who prematurely discontinue the study should be scheduled for the End of Study (EOS) visit within 7 days. At this final visit, all the assessments mentioned under EOS visit should be performed, all dispensed investigational product should be reconciled, and the

adverse event and concomitant medications recorded on the CRF. Participants that prematurely discontinue should also have a remote follow-up safety visit performed 30 days after the EOS visit.

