**Table 8-3 Assessment schedule for Cohorts 2 and 3 (Pfizer vaccine)**

Period	Screening	Treatment						Follow-up	
Visit Name	Visit 1 Screening	Visit 2	Visit 3	Visit 4	Visit 5	Visit 6	Visit 7/End of Study (EOS)	Visit 8 / Safety	Unscheduled
Day/Week/Month	Day -7	Day 1	Day 22	Day 36	Day 202	Day 292	Day 382	Day 412	
Visit Window				+3d	+/-3d	+/-3d	+/-3d	+/-3d	
Obtain informed consent	X								
Inclusion/exclusion criteria	X								
Demography	X								
Relevant medical history/current medical history	X								
Non-drug therapies and procedures	X	X	X	X	X	X	X	S	X
Prior/Concomitant Medications	X	X	X	X	X	X	X	S	X
MS Relapse	X	X	X	X	X	X	X	S	X
Serum Pregnancy Test 	S						S		

Period	Screening	Treatment						Follow-up	
Visit Name	Visit 1 Screening	Visit 2	Visit 3	Visit 4	Visit 5	Visit 6	Visit 7/End of Study (EOS)	Visit 8 / Safety	Unscheduled
Day/Week/Month	Day -7	Day 1	Day 22	Day 36	Day 202	Day 292	Day 382	Day 412	
Visit Window				+3d	+/-3d	+/-3d	+/-3d	+/-3d	
Hepatitis B virus (HBV) (Cohort 2 only) 	X								
SARS CoV2 qualitative antibody		X	X	X	X	X	X		
Serum Immunoglobulin 	X				X		X		
CD 19+ B cells (Cohort 2 only)	X	X	X	X	X	X	X		
Biobanked serum sample 	X			X					
Biobanked whole blood sample 	X			X					
Vaccine Administration Form		X	X						
IRT Transaction	X	X	X	X	X	X	X		
Drug Accountability		S	S	S	S	S	S		
Adverse Events / Serious Adverse Events	X	X	X	X	X	X	X	S	X
Subject disposition	X						X	S	

X = assessment to be recorded in the clinical database or received electronically from a vendor

S = assessment to be recorded in the source documentation only

 Serum pregnancy should be performed locally for all sites except those unable to use a local lab. Sites unable to perform locally should send sample to the central lab.

 Participants with lab results within the past 6 months prior to screening will not require labs drawn at screening visit. Local labs should be documented in the source. Participants without lab results from the past 6 months prior to screening will require central labs drawn at the screening visit to be entered into the clinical database.

 Sample will be bio-banked for yet to be identified analyses.

 Vaccine check-ins (remote contacts) by site staff to confirm participant has received the COVID-19 vaccine and to collect any AEs/SAEs.

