#### **8.5       Additional assessments**

No additional tests will be performed on participants entered into this study.

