2.1 Data analysis general information

The statistical analysis outlined in this SAP will be performed by [REDACTED], a Novartis-designated Contract Research Organization (CRO), using SAS® version 9.4 or higher.

For continuous variables, descriptive statistics will include number of participants (n), mean, standard deviation, minimum, maximum, median and 25th and 75th percentiles. For categorical variables, frequency counts and percentages will be reported. Where appropriate, 2-sided 95% confidence intervals (CIs) for point estimates of the mean or proportion will be provided.

Unless otherwise stated, all data summaries will be presented by **cohort group** (see below) and on all participants in the respective analysis set.

- Cohort 1
- Cohorts 2 and 4 combined
- Cohorts 3 and 5 combined
- Cohort 6

All data will be listed appropriately.

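### Immune conversion has no defined evaluable denominator: nucleocapsid-positive Cohort 4/5 participants and all of Cohort 6 have no route to 'yes', yet by default count as non-converters

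*SAP*

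**What the plan says.** SAP 2.6.1 defines immune conversion as a yes/no endpoint with three alternative routes:

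- First route: "Pre-vaccination absence of SARS-CoV-2 qualitative IgG antibody with" a positive result after vaccination.
- Second route, for antibody already present: "Pre-vaccination serum presence of SARS-CoV-2 quantitative IgG antibody with post-vaccination" at least a 4-fold titer rise.
- Third route, for Cohorts 4 and 5: "Initial negative SARS-CoV-2 nucleocapsid antibody at Visit 2 (Day 1) with post-vaccination positive SARS-CoV-2 qualitative IgG antibody assay", the positive result coming at an assessment after Visit 2.

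SAP 2.1.1 states that a pre-vaccination value exists only for Cohorts 1, 2 and 3.

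For reporting, SAP 2.1 presents summaries by cohort group and, unless stated otherwise, "on all participants in the respective analysis set". SAP 2.2 makes the Safety Analysis Set the default. SAP 2.6.2 reports conversion by cohort group and overall. SAP 2.6.6 adds an observed-case version and a repeat on Cohort 6 plus participants boosted during the study.

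On booster status, SAP Table 1 limits the third route to participants who have had no booster. SAP 2.6.1 carries no such condition. The protocol shows the same split between Table 2-1 and section 12.5.

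On prior infection, Protocol Amendment 2 was written to "allow participants with a known diagnosis of COVID-19 prior to starting in the study to be enrolled". The rationale for the study population in Protocol 4.1 still says people with evidence of prior COVID-19 are excluded.

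**The concern.** A participant who can meet none of the routes has an undetermined conversion status. That is different from failing to convert. If such participants sit in the denominator as 'No', the reported percentage falls with infection history and cohort membership as well as with vaccine response.

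These participants will occur. Amendment 2 admits known prior COVID-19, and the exclusion list in Protocol 5.2 has no criterion against past infection. The nucleocapsid test is scheduled at Visit 2 (Protocol Tables 8-5 and 8-6), so undiagnosed past infection comes to light only after screening. Cohort 6 is a planned 22 of 88 participants, and every one of them lacks a route.

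**Working it through.** **The plan's own figure.** The documents state no target or precision for conversion. The only design figure is the 95% interval half-width for 20 participants. It reproduces as 1.96 × √(p(1 − p)/20): 20.1% at p = 0.70, 19.0% at 0.75 and 17.5% at 0.80. This point does not affect it.

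**Tracing participants through SAP 2.6.1**

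| Participant | Route to 'yes' |
|---|---|
| Cohorts 1–3, antibody-negative before vaccination | First |
| Cohorts 1–3, antibody-positive before vaccination | Second (4-fold rise) |
| Cohorts 4/5, nucleocapsid-negative, unboosted | Third |
| Cohort 5, nucleocapsid-negative, boosted | Third under 2.6.1; none under Table 1 |
| Cohorts 4/5, nucleocapsid-positive | None |
| Cohort 6 | None |

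**Does any rule remove those without a route?** SAP 2.6.1 to 2.6.6 contain none, and SAP 5.5 says there are no exclusion rules for analysis sets. The observed-case analysis drops only missing assays. A nucleocapsid-positive participant with a valid positive IgG result stays in.

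**Ceiling within a group of 22.** With k participants who have no route, the highest possible rate is (22 − k)/22. The documents give no infection rate, so k is assumed.

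| k | Highest possible rate | Exact 95% interval at that rate |
|---|---|---|
| 2 | 20/22 = 90.9% | 70.8% to 98.9% |
| 4 | 18/22 = 81.8% | 59.7% to 94.8% |
| 7 | 15/22 = 68.2% | 45.1% to 86.1% |
| 9 | 13/22 = 59.1% | 36.4% to 79.3% |

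The groups are reported as Cohorts 2 and 4 and Cohorts 3 and 5. Cohort 2 and 3 members have the first two routes, so k can come only from the Cohort 4 or 5 members. If a share q of those members is nucleocapsid-positive, the ceiling is 1 − q when the whole group is Cohort 4 or 5. For q of 20% to 40% that is 80% to 60%. If half the group (assumed) comes from Cohort 2 or 3, it is 1 − q/2, or 90% to 80%.

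**Effect below the ceiling.** Suppose 75% of those with a route convert (assumed), and the whole group is Cohort 4 or 5. The reported rate is then 0.75 × (1 − q): 67.5% at q = 10%, 60.0% at 20%, 52.5% at 30% and 45.0% at 40%. If those without a route are left out of the denominator, it stays at 75%.

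**Cohort 6.** As its own group it can only report 0/22 (exact 95% interval 0 to 15.4%). In the overall row the maximum is (88 − 22)/88 = 66/88 = 75%. Each further participant without a route lowers that by 1/88, or 1.1 points.

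**The case against.** The nucleocapsid condition is deliberate and sensible. Without pre-vaccination serum, a negative nucleocapsid test is how the plan attributes antibody to the vaccine and not to infection. That stands. It is a reason not to call nucleocapsid-positive participants converters, but it gives no reason to call them failures.

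No sentence in the SAP says outright that they are scored 'No'. The denominator text allows for exceptions, and non-response imputation addresses missing assays, which a positive nucleocapsid result is not. This also stands: the scoring follows from a yes/no endpoint on a default analysis set. But no exception is written, so a programmer following the text arrives there.

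The endpoint is secondary, has no hypothesis test, and the same participants still contribute to the primary immune-response rate. That limits the consequence.

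A reader might go further in two ways that the documents do not support.

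- One might infer that antibody-positive participants in Cohorts 1 to 3 also fail automatically because the titer is never measured. Protocol section 8 says its tables "list all assessments with an X when they are performed", the readable row in Table 8-3 is "SARS CoV2 qualitative antibody", and Protocol 8.5 says "No additional tests will be performed on participants entered into this study". But these participants do have the 4-fold-rise route, and the Protocol summary names a combined qualitative and quantitative IgG assay. The available schedules are visibly incomplete: the text of Table 8-2 has no antibody row, and SAP Tables 4, 7 and 10 are not in the text. Protocol 8.5 goes on to describe further samples in 8.5.2 and 8.5.3. Nothing here shows that the titer is not collected.
- One might infer that the rule favours ofatumumab, on the argument that B-cell depletion blunts nucleocapsid antibody, so that fewer infected ofatumumab participants test positive. The documents give neither infection rates nor detection rates by treatment. A different ceiling in the two groups is possible, but its size cannot be determined.

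**Conclusion.** The point holds for nucleocapsid-positive participants in Cohorts 4 and 5 and for the whole of Cohort 6. Followed as written, the SAP counts them as non-converters irrespective of vaccine response. For Cohort 6 the size follows from planned enrolment alone: a fixed 0% in its own group and a cap of 75% overall. For the combined groups it depends on k, which is unknown until nucleocapsid results are in. Boosted Cohort 5 participants are unresolved because Table 1 and 2.6.1 disagree. No direction of bias between ofatumumab and control is established. The change should be made before the conversion tables are produced, but it does not touch the primary endpoint.

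**What to change.** In SAP 2.6.1 and 2.6.2, define a conversion-evaluable denominator:

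- Cohorts 1 to 3 with a pre-vaccination result;
- Cohorts 4 and 5 that are nucleocapsid-negative at Visit 2 and unboosted, as in Table 1.

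Report nucleocapsid-positive Cohort 4/5 participants, boosted Cohort 5 participants and Cohort 6 in a separate row, 'not evaluable for conversion', and not as 'No'. Apply the same rule to the overall row and to the repeat analyses in SAP 2.6.6.

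Bring SAP 2.6.1 into line with SAP Table 1 on booster status, and reconcile Protocol Amendment 2 with the study-population rationale in Protocol 4.1 on prior COVID-19.

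This is wording only, with no new samples. The cost is precision. By the plan's own half-width formula at a 75% rate, going from 22 to 18 evaluable participants widens the half-width from 1.96 × √(0.1875/22) = 18.1 points to 1.96 × √(0.1875/18) = 20.0 points.

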## 2 Objectives, endpoints and estimands

**Table 2-1 Objectives and related endpoints**

Objective(s)	Endpoint(s)
Primary Objectives	Endpoint(s) for primary objective(s)

 
To assess immune response to non-live mRNA COVID-19 vaccine in ofatumumab treated participants
 
	
 
Achieving immune response as defined by positive SARS-CoV-2 qualitative IgG antibody assay <math>\geq</math> 14 days after vaccination (yes/no)
 

Secondary Objectives	Endpoint(s) for secondary objective(s)

 
To assess sustained immune response to non-live mRNA COVID-19 vaccine in ofatumumab treated participants
 
To assess immune conversion to non-live mRNA COVID-19 vaccine in ofatumumab treated participants
 
	
 
Achieve immune response at other assessment time points (yes/no)
 
Immune conversion to non-live mRNA COVID-19 vaccine (yes/no) defined as : 
 
For patients with serum available prior to vaccine: 
 
Baseline absence of SARS-CoV-2 spike IgG with post-vaccination SARS-CoV-2 positive qualitative antibody assay <math>\geq</math> 14 days after full course (two doses) vaccination (yes/no) or
 
Baseline serum presence of SARS-CoV-2 quantitative IgG antibody with post-vaccination <math>\geq</math> 4-fold increase in SARS-CoV-2 quantitative antibody titer as determined by dilution assay <math>\geq</math> 14 days after vaccination (yes/no)
 
 
 
For patients with serum unavailable prior to vaccine but who have not received a booster (Cohorts 4 and 5): 
 
Initial negative SARS-CoV-2 nucleocapsid antibody with post-vaccination SARS-CoV-2 positive qualitative antibody assay <math>\geq</math> 14 days after full course (two doses) vaccination (yes/no)
 
 
 
 
 

 
To assess adverse events and serious adverse events
 
	
 
Adverse events/serious adverse events
 

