5. Completed a full course (two doses) of a COVID-19 mRNA vaccine at least  $\geq 4$  weeks after start of commercially prescribed ofatumumab for the treatment of RMS
6. Currently on commercially prescribed ofatumumab for  $\geq 4$  weeks for the treatment of RMS
7. Received two dose mRNA COVID-19 vaccine (Pfizer or Moderna vaccine)  $\geq 2$  weeks ago
8. Pre-ofatumumab serologies with Hepatitis B testing not indicative of active or latent infection
9. Total serum immunoglobulin IgG  $\geq 400$  mg/dl at Screening

Patients eligible for inclusion in Cohort 5 of this study must meet **all** of the following criteria:

1. Signed informed consent must be obtained prior to participation in the study
2. Age 18-55 years old at Screening
3. Diagnosis of relapsing MS by 2017 revised McDonald criteria
4. Must be willing to comply with the study schedule
5. Currently on commercially prescribed interferon or glatiramer acetate for  $\geq 4$  weeks for the treatment of RMS
6. Completed a full course (two doses) of a COVID-19 mRNA vaccine after start of glatiramer acetate or interferon
7. Received two dose mRNA COVID-19 vaccine (Pfizer or Moderna vaccine)  $\geq 2$  weeks ago
8. If the patient has received the mRNA booster, then the mRNA booster should be  $\geq 2$  weeks prior to enrollment.
9. Total serum immunoglobulin IgG  $\geq 400$  mg/dl at Screening

Patients eligible for inclusion in Cohort 6 of this study must meet **all** of the following criteria:

1. Signed informed consent must be obtained prior to participation in the study
2. Age 18-55 years old at Screening
3. Diagnosis of relapsing MS by 2017 revised McDonald criteria
4. Must be willing to comply with the study schedule
5. Currently on commercially prescribed ofatumumab for  $\geq 4$  weeks for the treatment of RMS

6. Completed a full course (two doses) of a COVID-19 mRNA vaccine at least  $\geq$  4 weeks after start of commercially prescribed ofatumumab for the treatment of RMS
7. Received two dose mRNA COVID-19 vaccine (Pfizer or Moderna vaccine)  $\geq$  2 weeks ago
8. Pre-ofatumumab serologies with Hepatitis B testing not indicative of active or latent infection
9. Total serum immunoglobulin IgG  $\geq$  400 mg/dl at Screening
10. Has received an mRNA booster  $\geq$  2 weeks prior to enrollment

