Cohort 2: Relapsing MS participants receiving a full course (2 doses) of a non-live COVID-19 mRNA vaccine ≥4 weeks after ofatumumab start.

Will continue taking their prescribed ofatumumab as per their current dosing schedule.

Cohort 3: Relapsing MS participants receiving a full course (2 doses) of a non-live COVID-19 mRNA vaccine ≥4 weeks after start of prescribed interferon or glatiramer acetate.

Will continue administration of their prescribed interferon or glatiramer acetate as per their current dosing schedule.

Cohort 4: Relapsing MS participants having completed a full course (2 doses) of a non-live COVID-19 mRNA vaccine ≥4 weeks after ofatumumab start.

Will continue taking their prescribed ofatumumab as per their current dosing schedule.

Cohort 5: Relapsing MS participants having completed a full course (2 doses) of a non-live COVID-19 mRNA vaccine ≥4 weeks after glatiramer acetate or interferon start.

Will continue taking their prescribed glatiramer acetate or interferon as per their current dosing schedule.

Cohort 6: Relapsing MS participants having completed a full course (2 doses) of a non-live COVID-19 mRNA vaccine ≥4 weeks after ofatumumab start and having received a booster ≥14 days prior to screening.

Will continue taking their prescribed ofatumumab as per their current dosing schedule.

Study completion

According to the protocol, study completion is defined as when the last participant completes the end of study (EOS) visit. Participants who discontinue study treatment or who decide they do not wish to participate in the study further should NOT be considered withdrawn from the study UNLESS they withdraw their consent. Where possible, they should return for the EOS visit.

Study design schematics for Cohorts 1, 2 and 3 are shown in Figures 1, 2, 3 and 4. Study design schematics for Cohorts 4, 5 and 6 are shown in Figures 5 and 6.

Figure 1 Study Design (Cohort 1, Pfizer)

[figure not shown]

Figure 2 Study Design (Cohort 1, Moderna)

[figure not shown]

Figure 3 Study Design (Cohorts 2 and 3, Pfizer)

[figure not shown]

Figure 4 Study Design (Cohorts 2 and 3, Moderna)

[figure not shown]

Figure 5 Study Design (Cohorts 4, 5 and 6, Pfizer)

[figure not shown]
[figure not shown]

Figure 6 Study Design (Cohorts 4, 5 and 6, Moderna)

Primary analysis time point

The primary analysis time point is Visit 4 for Cohorts 1, 2 and 3, and Visit 2 for Cohorts 4, 5 and 6.

Interim analysis

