1.2 Study objectives, endpoints and estimands

Study objectives and associated endpoints are shown in Table 1.

Table 1 Study objectives and endpoints

Objective(s)	Endpoint(s)
Primary Objective(s) 
To assess immune response to non-live mRNA COVID-19 vaccine in ofatumumab-treated participants	Endpoint(s) for primary objective(s) 
Achieving immune response as defined by positive severe acute respiratory syndrome coronavirus 2 (SARS-CoV-2) qualitative Immunoglobulin G (IgG) antibody assay ≥ 14 days after full course (2 doses) vaccination (yes/no)
Secondary Objective(s) 
To assess sustained immune response to non-live mRNA COVID-19 vaccine in ofatumumab-treated participantsTo assess immune conversion to non-live mRNA COVID-19 vaccine in ofatumumab-treated participants	Endpoint(s) for secondary objective(s) 
Achieving immune response at other assessment time points (yes/no)Immune conversion to non-live mRNA COVID-19 vaccine (yes/no) defined as:
For participants with serum available prior to vaccination:
Pre-vaccination absence of SARS-CoV-2 spike IgG with post-vaccination SARS-CoV-2 positive qualitative antibody assay ≥ 14 days after full course (2 doses) vaccination (yes/no) orPre-vaccination serum presence of SARS-CoV-2 quantitative IgG antibody with post-vaccination ≥ 4-fold increase in SARS-CoV-2 quantitative antibody titer as determined by dilution assay ≥ 14 days after full course (2 doses) vaccination (yes/no)For participants with serum unavailable prior to vaccination and who have not received a booster (Cohorts 4 and 5):
Initial negative SARS-CoV-2 nucleocapsid antibody with post-vaccination SARS-CoV-2 positive qualitative antibody assay ≥ 14 days after full course (2 doses) vaccination (yes/no)

Objective(s)	Endpoint(s)

• To assess adverse events and serious adverse events	
• Adverse events/serious adverse events

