Pfizer vaccine:			
Pre-vaccination	Day 1	1	≤1
14 days post-vaccination	Day 36	36	(vaccine day + 1) to 64
70 days post-vaccination	Day 92	92	65 to 147
180 days post-vaccination	Day 202	202	148 to 292
360 days post-vaccination	Day 382	382	≥293
Moderna vaccine:			
Pre-vaccination	Day 1	1	≤1
14 days post-vaccination	Day 43	43	(vaccine day + 1) to 71
70 days post-vaccination	Day 99	99	72 to 154
180 days post-vaccination	Day 209	209	155 to 299
360 days post-vaccination	Day 389	389	≥300

Note:

- Pre-vaccination and study day are derived as outlined in [Section 2.1.1](#).
- Vaccine day is the study day of the second dose of the COVID-19 vaccine.
- Assessments performed between the first and second doses of the COVID-19 vaccine are not assigned an analysis visit.

[figure not shown]

Table 5**Cohorts 2 and 3 visit windows for SARS-CoV-2 qualitative antibody / CD19+ B cells (Cohort 2 only) / T cell**

Analysis visit	Nominal time point	Scheduled visit day (target study day)	Visit window (study days)
Pfizer vaccine:			
Pre-vaccination	Day 1	1	≤1
14 days post-vaccination	Day 36	36	(vaccine day + 1) to 119
180 days post-vaccination	Day 202	202	120 to 247
270 days post-vaccination	Day 292	292	248 to 337
360 days post-vaccination	Day 382	382	≥338
Moderna vaccine:			
Pre-vaccination	Day 1	1	≤1
14 days post-vaccination	Day 43	43	(vaccine day + 1) to 126
180 days post-vaccination	Day 209	209	127 to 254
270 days post-vaccination	Day 299	299	255 to 344
360 days post-vaccination	Day 389	389	≥345

Note:

- Pre-vaccination and study day are derived as outlined in [Section 2.1.1](#).
- Vaccine day is the study day of the second dose of the COVID-19 vaccine.
- Assessments performed between the first and second doses of the COVID-19 vaccine are not assigned an analysis visit.

Table 6**Cohorts 2 and 3 visit windows for serum immunoglobulin (IgG, IgM)**

Analysis visit	Nominal time point	Scheduled visit day (target study day)	Visit window (study days)
Pfizer vaccine:			
Pre-vaccination	Day 1	1	≤1
180 days post-vaccination	Day 202	202	(vaccine day + 1) to 292
360 days post-vaccination	Day 382	382	≥293
Moderna vaccine:			
Pre-vaccination	Day 1	1	≤1
180 days post-vaccination	Day 209	209	(vaccine day + 1) to 299
360 days post-vaccination	Day 389	389	≥300

Note:

- Pre-vaccination and study day are derived as outlined in [Section 2.1.1](#).
- Vaccine day is the study day of the second dose of the COVID-19 vaccine.

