- Assessments performed between the first and second doses of the COVID-19 vaccine are not assigned an analysis visit.

Table 8**Cohorts 4, 5 and 6 visit windows for SARS-CoV-2 qualitative antibody / CD19+ B cells (Cohorts 4 and 6 only) / T cell**

Analysis visit	Nominal time point	Scheduled visit day (target study day)	Visit window (study days)
Pfizer vaccine:			
14 days post-vaccination	Day 1	1	(vaccine day + 1) to 1
180 days post-vaccination	Day 202	202	2 to 247
270 days post-vaccination	Day 292	292	248 to 337
360 days post-vaccination	Day 382	382	≥338
Moderna vaccine:			
14 days post-vaccination	Day 1	1	(vaccine day + 1) to 1
180 days post-vaccination	Day 209	209	2 to 254
270 days post-vaccination	Day 299	299	255 to 344
360 days post-vaccination	Day 389	389	≥345

Note:

[figure not shown]
- Study day is derived as outlined in [Section 2.1.1](#).
- Vaccine day is the study day of the second dose of the COVID-19 vaccine for Cohorts 4 and 5, and the study day of the COVID-19 vaccine booster for Cohort 6.

Table 9 **Cohorts 4, 5 and 6 visit windows for serum immunoglobulin (IgG, IgM)**

Analysis visit	Nominal time point	Scheduled visit day (target study day)	Visit window (study days)
Pfizer vaccine:			
14 days post-vaccination	Day 1	1	(vaccine day + 1) to 1
180 days post-vaccination	Day 202	202	2 to 292
360 days post-vaccination	Day 382	382	≥293
Moderna vaccine:			
14 days post-vaccination	Day 1	1	(vaccine day + 1) to 1
180 days post-vaccination	Day 209	209	2 to 299
360 days post-vaccination	Day 389	389	≥300

Note:

- Study day is derived as outlined in [Section 2.1.1](#).
- Vaccine day is the study day of the second dose of the COVID-19 vaccine for Cohorts 4 and 5, and the study day of the COVID-19 vaccine booster for Cohort 6.

Multiple assessments

When there are multiple assessments in a particular visit window, the rules outlined below are applied to select one value “representing” the participant in summary statistics for that visit window. All assessments will be displayed in listings.

- **Pre-vaccination (only applicable to Cohorts 1, 2 and 3):** Pre-vaccination is derived as outlined in [Section 2.1.1](#). In situations where the same assessment is performed more than once on Study Day 1 the repeated assessment will be used.
- **Post-vaccination:** For post-vaccination visit windows, the following rules apply (unless otherwise specified):

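### For Cohorts 4 and 5, SAP 2.6.1 excludes the Visit 2 IgG from immune conversion, although SAP Table 1 and the protocol allow it to count

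*SAP*

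**What the plan says.** SAP 2.6.1 gives three routes to immune conversion. The first two compare post-vaccination with pre-vaccination serum and accept any assessment at least 14 days after the two-dose course. The third, for Cohorts 4 and 5, requires a negative nucleocapsid antibody at Visit 2 and a positive "SARS-CoV-2 qualitative IgG antibody assay at any post-Visit 2 (Day 1) assessment time point", also at least 14 days after the course.

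SAP Table 1 describes the same endpoint under the heading "For participants with serum unavailable prior to vaccination and who have not received a booster (Cohorts 4 and 5"), with no requirement that the IgG sample come after Visit 2. Protocol Table 2-1 has "Initial negative SARS-CoV-2 nucleocapsid antibody with post-vaccination SARS-CoV-2 positive qualitative antibody assay" at least 14 days after the full course. Protocol 12.5 is worded almost identically. Neither protocol section mentions Visit 2.

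For these cohorts, SAP 1.1 sets the primary analysis time point at "Visit 2 for Cohorts 4, 5 and 6". Conversion is summarised by cohort group and overall (SAP 2.6.2), with Cohort 2 pooled with 4 and Cohort 3 with 5 (SAP 2.1). SAP section 4 states that nothing in the protocol-specified analyses has changed.

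**The concern.** The SAP defines one endpoint in two ways, and a programmer following 2.6.1 can get different counts from one following Table 1. The excluded sample is the one that decides the primary endpoint in Cohorts 4 and 5. It is also the only scheduled IgG in those cohorts with a nucleocapsid result from the same visit. Later samples have no repeat nucleocapsid test, and protocol 12.5 recognises that boosters may be given during the trial.

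Within each pooled row, one part can use the response at the 14-day analysis visit. The other part must be positive at a later draw, which is closer to the separate objective of sustained response. Converters may then be undercounted in Cohorts 4 and 5 and, through the pooling, in the combined rows.

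**Working it through.** **Does the Visit 2 sample qualify under Table 1 and the protocol?**

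- Protocol 5.1, Cohorts 4 and 5: "Received two dose mRNA COVID-19 vaccine (Pfizer or Moderna vaccine") at least 2 weeks earlier. A Visit 2 sample is therefore post-vaccination and at least 14 days after the course.
- SAP 2.4.1.1, Table 8 ("Cohorts 4, 5 and 6 visit windows for SARS-CoV-2 qualitative antibody"): the window ending on Day 1 carries the 14-day post-vaccination label.
- SAP 2.4.1.1, Table 5 ("Cohorts 2 and 3 visit windows for SARS-CoV-2 qualitative antibody"): the Day 36 (Pfizer) or Day 43 (Moderna) draw carries the same label, and under route 1 it counts towards conversion.

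So the Visit 2 sample qualifies under Table 1 and the protocol, and only SAP 2.6.1 excludes it.

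**Which scheduled IgG draws count under SAP 2.6.1?**

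| Cohorts | Source | Post-dose-2 draws, Pfizer / Moderna | Eligible |
|---|---|---|---|
| 2 and 3 | Protocol Tables 8-3, 8-4 | Days 36, 202, 292, 382 / 43, 209, 299, 389 | 4 of 4 |
| 4 and 5 | Protocol Tables 8-5, 8-6 | Days 1, 202, 292, 382 / 1, 209, 299, 389 | 3 of 4 (not Day 1) |

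Gap from Visit 2 to the first eligible scheduled draw: 202 − 1 = 201 days (Pfizer) and 209 − 1 = 208 days (Moderna). For someone who leaves early it can be shorter: "Participants who prematurely discontinue the study should be scheduled for the End of Study (EOS) visit within 7 days", and that visit includes the IgG assay. A positive result there counts.

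**Direction.** Table 1 sets no upper time limit. The draws allowed by 2.6.1 are a subset of those allowed by Table 1, so every 2.6.1 converter is also a Table 1 converter. The restriction can remove converters but not add any.

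**Do the missing-data rules repair it?** Under non-response imputation (SAP 2.6.3, 2.6.4), a missing later assay is scored No. In the observed-case repeat (SAP 2.6.6), a participant with only negative later assays stays No, and one with no later assay drops out. Neither analysis restores the Visit 2 positive.

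**Size.** Each affected participant lowers a group of 22 by 1/22 = 4.5 points. The documents give neither the Cohort 2/4 and 3/5 splits nor the rates of loss or reversion to negative. As an assumption, let 16 of 22 convert under Table 1, and let k of them have their only positive IgG at Visit 2. With exact (Clopper-Pearson) 95% intervals:

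| k | Converters under 2.6.1 | Rate | 95% CI |
|---|---|---|---|
| 0 | 16/22 | 72.7% | 49.8 to 89.3 |
| 1 | 15/22 | 68.2% | 45.1 to 86.1 |
| 2 | 14/22 | 63.6% | 40.7 to 82.8 |
| 3 | 13/22 | 59.1% | 36.4 to 79.3 |

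**Two related gaps in 2.6.1.** The no-booster condition in SAP Table 1 and protocol Table 2-1 is not repeated. Cohort 6 has no route to conversion, yet no sentence takes it out of the summaries or out of the 2.6.6 repeat, which uses Cohort 6 data. If Cohort 6 were coded No on the full denominator, the overall rate could not exceed (88 − 22)/88 = 75%. The SAP does not prescribe that coding; it leaves the matter open.

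**The case against.** The restriction may be deliberate. The SAP change log lists 2.6.1 among the sections updated for Cohorts 4 and 5, and requiring the negative result first and the positive one later imposes a time order. Without it, route 3 can be met at a single visit and shows no change over time. This has some force, but all samples in these cohorts are post-vaccination, so a later draw does not create a before/after comparison with vaccination either. A deliberate restriction would still have to appear in Table 1 and be declared.

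Some of the difference within the pooled groups would remain after the fix. Cohorts 2 and 3 are judged against pre-vaccination serum and Cohorts 4 and 5 by nucleocapsid status, as the protocol intends. The interval between dose 2 and Visit 2 in Cohorts 4 and 5 has no upper limit, so equal labels in Tables 5 and 8 do not mean equal timing. Both points stand.

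The one-way direction depends on reading Table 1 as open-ended. If it meant only the 14-day time point, 2.6.1 could also add late converters. The wording sets a minimum of 14 days and no maximum, so the open-ended reading is the natural one.

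The SAP cites protocol version 01 of 29-Sep-2021, while the protocol supplied includes Amendment 2. The no-change statement in section 4 may therefore refer to another version. The conflict between SAP Table 1 and SAP 2.6.1 does not depend on this.

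The Cohort 6 and booster points are largely answered elsewhere: the routes as written do not reach Cohort 6, Table 1 states the booster condition, and Cohort 4 is unboosted at entry by definition. They are points of wording.

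**Conclusion.** The concern holds. SAP 2.6.1 conflicts with SAP Table 1 and with the protocol supplied, and followed literally it scores some primary responders as non-converters. The loss is 4.5 points per affected participant in a group of 22. The number affected is unknown and may be zero, and the 16/22 starting point is illustrative. The denominator of 22 assumes full enrolment and nobody left out; excluding boosted Cohort 5 participants would make the 3+5 group smaller and each loss larger.

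The effect is confined to immune conversion, a descriptive secondary endpoint with no hypothesis test. The Visit 2 IgG still determines the primary endpoint in these cohorts. The inconsistency should be corrected before the analysis is programmed, but it does not threaten the main result.

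**What to change.** Delete the post-Visit 2 condition from route 3 of SAP 2.6.1, so that it matches SAP Table 1 and the protocol and the Visit 2 IgG counts. If the restriction is intended, declare and justify it in SAP section 4, correct Table 1, and report conversion with the Visit 2 IgG included alongside the restricted version.

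In the same edit, state that conversion does not apply to Cohort 6, removing it from the conversion rows, the overall denominator and the 2.6.6 repeat of that endpoint. Carry the no-booster condition from Table 1 into 2.6.1, or reconcile the two.

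The cost is SAP wording and programming; no new data are needed. There are two trade-offs. Route 3 could be met at a single visit, so a table footnote should say that it shows no before/after change as routes 1 and 2 do. Leaving out Cohort 6 and boosted Cohort 5 participants reduces the denominators and widens the intervals.
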